10.7.2. Secondary Endpoints

10.7.2.3 Viral Load Endpoints

Peak Viral Load of RSV as Defined by the Maximum Viral Load Determined by qRT-PCR Measurements in Nasal Samples Starting from Initial Administration of IMP up to Planned Discharge from Quarantine

Using the scheduled protocol assessments from the last measurement collected prior to the first dose of IMP to morning of Day 12 (Quarantine discharge), the highest qRT-PCR viral load value observed in nasal samples for each participant will be summarised and analysed in a similar fashion to the primary efficacy endpoint described in Section 10.7.1.

Participants who stay undetectable (i.e. a 'Not Detected' value) during quarantine will be replaced with the 'Not Detected' value shown in the table in Appendix 15.1.

Time to Confirmed Negative Test by qRT-PCR Measurements in Nasal Samples Starting from Initial Administration of IMP to First Confirmed Undetectable Assessment after Peak Measure

The time from the first administration of IMP to the first confirmed negative qRT-PCR test after the peak qRT-PCR measurement will be calculated in days as:

Date and time of first confirmed negative test after peak qRT-PCR measurement – Date of and time of first IMP administration.

A negative test is defined as two consecutive 'Not Detected' results in the qRT-PCR test, with the date and time of the first negative test being utilised in the calculations. The peak qRT-PCR is defined as the highest viral load value obtained by a participant after their first administration of IMP.

Participants who did not have a confirmed undetectable assessment after first administration of IMP are censored at their last detectable assessment after their peak qRT-PCR measurement. Participants who stay undetectable during quarantine will be excluded from this analysis. Participants who return a positive result after two consecutive 'not detected' results will remain within the analysis.

The time to confirmed negative test will be summarised descriptively by treatment group. Kaplan Meier [2] curves will be produced for each treatment group, overlayed on one plot. A supporting table will include the median, 25th and 75th percentiles for each group and will be accompanied by a log rank test to compare between RV299 and placebo with the corresponding p-value presented.

[Kaplan-Meier plot: y-axis = cumulative proportion of participants without a negative test, x-axis = day relative to initial administration of IMP, one line for each treatment overlayed on the same plot].

Time to Confirmed Negative Test by qRT-PCR Measurements in Nasal Samples Starting from Peak qRT-PCR after Initial Administration of IMP to First Confirmed Undetectable Assessment after Peak Measure

The time from the peak qRT-PCR measurement after administration of IMP to the first confirmed negative qRT-PCR test will be calculated in days as:

Date and time of first confirmed negative test – Date and time of first IMP administration.

A negative test is defined as two consecutive 'Not Detected' results in the qRT-PCR test, with the date and time of the first negative test being utilised in the calculations. The peak qRT-PCR is defined as the highest viral load value obtained by a participant after their first administration of IMP.

Participants who did not have a confirmed undetectable assessment after their peak qRT-PCR after first administration of IMP are censored at their last detectable assessment. Participants who stay undetectable during quarantine will be excluded from this analysis.

The time to confirmed negative test will be summarised descriptively by treatment group. Kaplan Meier curves will be produced for each treatment group, overlayed on one plot. A supporting table will include the median, 25th and 75th percentiles for each group and will be accompanied by a log rank test to compare between RV299 and placebo with the corresponding p-value presented.

[Kaplan-Meier plot: y-axis = cumulative proportion of participants without a negative test, x-axis = day relative to initial administration of IMP, one line for each treatment overlayed on the same plot].

Time to Peak qRT-PCR in Nasal Samples Starting from Initial Administration of IMP

The time to the peak qRT-PCR measurement starting from the initial administration of IMP will be calculated in days as:

Date and time of peak qRT-PCR measurement – Date and time of first IMP administration.

The peak qRT-PCR measurement is defined as the highest viral load value obtained by a participant after their first administration of IMP. Participants who stay undetectable during quarantine will be excluded from this analysis.

The time to peak qRT-PCR measurement will be summarised descriptively by treatment group. Kaplan Meier curves will be produced for each treatment group, overlayed on one plot. A supporting table will include the median, 25th and 75th percentiles for each group and will be accompanied by a log rank test to compare between RV299 and placebo with the corresponding p-value presented.

[Kaplan-Meier plot: y-axis = cumulative proportion of participants not yet reaching peak qRT-PCR, x-axis = day relative to initial administration of IMP, one line for each treatment overlayed on the same plot].

Area under the Viral Load-Time Curve (VL-AUC) of RSV Challenge Virus as Determined by Viral Culture in Nasal Samples, Starting from Initial Administration of IMP up to Planned Discharge from Quarantine

The area under the viral-load curve (VL-AUC) for RSV-A Memphis 37b measured in nasal washes by viral culture, from the last measurement collected prior to the first dose of IMP until the morning of Day 12 (Quarantine discharge) will be summarised and analysed as described in Section 10.7.1.

Viral culture analysis is only carried out on samples where the qRT-PCR results is at least detectable. Any missing viral culture results will be imputed with 'Not Detected' if the corresponding qRT-PCR result is not detected.

Peak Viral Load of RSV as Defined by the Maximum Viral Load determined by Viral Culture Measurements in Nasal Samples Starting from Initial Administration of IMP up to Planned Discharge From Quarantine

Using the scheduled protocol assessments from the last measurement collected prior to the first dose of IMP to the morning of Day 12 (Quarantine discharge), the highest viral culture measurement observed in nasal samples for each participant will be summarised and analysed in a similar fashion to the primary efficacy endpoint described in Section 10.7.1.

Participants who stay undetectable (i.e. a 'Not Detected' value) during quarantine will be replaced with the 'Not Detected' value shown in the table in Appendix 15.1.

Time to Confirmed Negative Test by Viral Culture Measurements in Nasal Samples Starting from Initial Administration of IMP to First Confirmed Undetectable Assessment after Peak Measure

The time from the first administration of IMP to the first confirmed negative viral culture measurement after the peak viral culture measurement will be calculated in days as:

Date and time of first confirmed negative test after peak viral culture measurement – Date and time of first IMP administration.

A negative test is defined as a 'Not Detected' result in the viral culture test, with the date and time of the first negative test being utilised in the calculations. The peak viral culture measurement is defined as the highest viral load value obtained by a participant after their first administration of IMP. Participants who did not have a confirmed undetectable assessment after first administration of IMP are censored at their last detectable assessment after their peak viral culture measurement. Participants who stay undetectable during quarantine will be excluded from this analysis.

The time to the confirmed negative test will be summarised descriptively by treatment group. Kaplan Meier curves will be produced for each treatment group, overlayed on one plot. A supporting table will include the median, 25th and 75th percentiles for each group and will be accompanied by a log rank test to compare between RV299 and placebo with the corresponding p-value presented.

[Kaplan-Meier plot: y-axis = cumulative proportion of participants without a negative test, x-axis = day relative to initial administration of IMP, one line for each treatment overlayed on the same plot].

Time to Confirmed Negative Test by Viral Culture Measurements in Nasal Samples Starting from Peak Viral Culture after Initial Administration of IMP to First Confirmed Undetectable Assessment after Peak Measure

The time from the peak viral culture measurement after administration of IMP to the first confirmed negative viral culture measurement will be calculated in days as:

Date of and time first confirmed negative test – Date and time of first IMP administration.

A negative test is defined as two consecutive 'Not Detected' results in the viral culture test, with the date and time of the first negative test being utilised in the calculations. The peak viral culture measurement is defined as the highest viral load value obtained by a participant after their first administration of IMP. Participants who did not have a confirmed undetectable assessment after their peak viral culture measurement after first administration of IMP are censored at their last detectable assessment. Participants who stay undetectable during quarantine will be excluded from this analysis.

The time to confirmed negative test will be summarised descriptively by treatment group. Kaplan Meier curves will be produced for each treatment group, overlayed on one plot. A supporting table will include the median, 25th and 75th percentiles for each group and will be accompanied by a log rank test to compare between RV299 and placebo with the corresponding p-value presented.

[Kaplan-Meier plot: y-axis = cumulative proportion of participants without a negative test, x-axis = day relative to initial administration of IMP, one line for each treatment overlayed on the same plot].

Time to Peak qRT-PCR in Nasal Samples Starting from Initial Administration of IMP

The time to the peak qRT-PCR measurement starting from the initial administration of IMP will be calculated in days as:

Date and time of peak qRT-PCR measurement – Date and time of first IMP administration.

The peak qRT-PCR measurement is defined as the highest viral load value obtained by a participant after their first administration of IMP. Participants who stay undetectable during quarantine will be excluded from this analysis.

The time to peak qRT-PCR measurement will be summarised using a descriptive summary. Kaplan Meier curves will be produced for each treatment group, overlayed on one plot. A supporting summary table will include the median, 25th and 75th percentiles for each group and will be accompanied by a log rank test to compare between RV299 and placebo with the corresponding p-value presented.

[Kaplan-Meier plot: y-axis = cumulative proportion of participants not yet reaching peak qRT-PCR, x-axis = day relative to initial administration of IMP, one line for each treatment overlayed on the same plot].

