7.2. Secondary Endpoints

The secondary endpoints are:

- Additional viral load endpoints relating to antiviral effect include but are not limited to:
 - Peak viral load of RSV as defined by the maximum viral load determined by qRT-PCR measurements in nasal samples starting from initial administration of IMP up to planned discharge from quarantine (Day 12, am).
 - Time (days) to confirmed negative test by qRT-PCR measurements in nasal samples starting at initial administration of IMP to first confirmed undetectable assessment after peak measure.
 - Time (days) to confirmed negative test by qRT-PCR measurements in nasal samples starting from peak qRT-PCR after initial administration of IMP to first confirmed undetectable assessment after peak measure.
 - Time (days) to peak qRT-PCR in nasal samples, starting from initial administration of IMP.
 - Area under the viral load-time curve (VL-AUC) of RSV challenge virus as determined by viral culture on nasal samples, starting at initial administration of IMP up to planned discharge from quarantine (Day 12, am).
 - Peak viral load of RSV as defined by the maximum viral load determined by viral culture measurements in nasal samples starting from initial administration of IMP up to planned discharge from quarantine (Day 12, am).
 - Time (days) to confirmed negative test by viral culture measurements in nasal samples starting at initial administration of IMP to first confirmed undetectable assessment after peak measure.
 - Time (days) to confirmed negative test by viral culture measurements in nasal samples starting from peak viral culture after initial administration of IMP to first confirmed undetectable assessment after peak measure.
 - Time (days) to peak viral culture in nasal samples, starting from initial administration of IMP.
- Clinical symptom-related endpoints include, but are not limited to:
 - Area under the curve over time of total clinical symptoms (TSS-AUC) as measured from 10 symptoms within the graded symptom scoring system collected 3 times daily starting at initial administration of IMP up to planned discharge from quarantine (Day 12, am).
 - Area under the curve over time of total clinical symptoms change from baseline (TSS-AUCCFB) as measured from 10 symptoms within the graded symptom scoring system

collected 3 times daily starting at initial administration of IMP up to planned discharge from quarantine (Day 12, am).

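### Peak viral load is taken over a window that includes the last pre-dose sample, while the time endpoints use a post-dose peak; this pulls the peak comparison toward no difference

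*SAP*

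**What the plan says.** The endpoint in SAP 7.2 is "Peak viral load of RSV as defined by the maximum viral load determined by qRT-PCR measurements in nasal samples starting from initial administration of IMP", ending at Day 12 am; protocol Section 3 defines it the same way. SAP 10.7.2.3 derives it "Using the scheduled protocol assessments from the last measurement collected prior to the first dose of IMP to morning of Day 12". The culture version has the same window: "Using the scheduled protocol assessments from the last measurement collected prior to the first dose of IMP to the morning of Day 12". Both peaks are analysed like the primary endpoint, by ANCOVA with a Wilcoxon rank-sum fallback. For qRT-PCR the covariate described in SAP 10.7.1 is the value of that same last pre-dose sample.

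The time endpoints in 10.7.2.3 use another peak. For time to confirmed negative: "The peak qRT-PCR is defined as the highest viral load value obtained by a participant after their first administration of IMP". For time to peak: "The peak qRT-PCR measurement is defined as the highest viral load value obtained by a participant after their first administration of IMP". The culture time-to-negative derivations also take the peak from values after the first dose.

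SAP 10.1.1 sets a general rule that, for most efficacy endpoints, the first value used is the one taken at the time of first dosing. The primary AUC and the culture AUC both start at the last pre-dose sample.

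**The concern.** An AUC needs a value at its left edge, so starting it at the pre-dose sample is natural. A maximum has no such need. Treatment cannot change a sample collected before the first dose. If that sample is the highest, it becomes the recorded peak, however far RV299 has lowered everything after it. An effective drug makes this happen more often in the RV299 arm, so the error runs in one direction, toward no difference, on an endpoint that is formally tested.

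The outputs can also disagree. When the pre-dose sample is the highest, a participant's peak value comes from one sample and the peak time from another. Listing 16.2.6.1.2 prints both in the same row.

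**Working it through.** The visible text gives no effect size, SD or power for this endpoint, so there is no plan figure to reproduce. The check sizes the floor under stated assumptions.

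**Inputs from the documents.** 40 participants per arm (SAP 6.1); 65% to 85% infected (protocol 2.3), so 0.65 × 40 = 26 to 0.85 × 40 = 34 per arm in ITT-I; two-sided 5% tests (SAP 10.1.4).

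**Assumptions.** Let B be the pre-dose value and P the highest post-dose value. On placebo the rise P − B is normal with mean r = 1, 2 or 3 log10 and SD s = 1.2 log10. RV299 lowers P by d = 1, 1.5 or 2 log10.

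**Formula.** The SAP peak is max(B, P) = B + max(0, P − B). B has the same mean in both arms, so the measured reduction is

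E[max(0, X₀)] − E[max(0, X₁)], with X₀ ~ N(r, s²) and X₁ ~ N(r − d, s²),

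where E[max(0, X)] = mΦ(m/s) + sφ(m/s) for mean m. A post-dose-only peak measures d itself.

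**Worked case, r = 2, d = 1.5.** Placebo: m = 2 gives 2.024. RV299: m = 0.5 gives 0.770. Measured reduction 2.024 − 0.770 = 1.254 in place of 1.5, a loss of 1 − 1.254/1.5 = 16%.

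| Placebo rise r | d = 1 | d = 1.5 | d = 2 |
|---|---|---|---|
| 1 log10 | 0.66 (loss 34%) | 0.87 (42%) | 1.00 (50%) |
| 2 log10 | 0.89 (11%) | 1.25 (16%) | 1.55 (23%) |
| 3 log10 | 0.98 (2%) | 1.44 (4%) | 1.87 (7%) |

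The chance that the pre-dose sample is the maximum is Φ(−r/s) on placebo and Φ(−(r − d)/s) on RV299. With r = 1 and d = 1 these are 20% and 50%.

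**Wider range.** With s from 1.0 to 1.5 and d from 0.5 to 2 log10, the share of the effect retained is 33–60% at a rise of 0.5 log10, 50–77% at 1, 73–96% at 2 and 89–100% at 3.

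**Does adjustment remove it?** No. I simulated the planned ANCOVA with B as covariate (B: mean 3.5, SD 1.5 log10, also assumed), 26 per arm and d = 1. The adjusted difference under the SAP definition was about −0.66, −0.89 and −0.98 at rises of 1, 2 and 3 log10, against about −1.0 for the post-dose-only peak.

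**Power, same settings.** ANCOVA power for the post-dose-only peak is about 0.83. The SAP definition lowers it by about 6 points at a rise of 1 log10, 2 at a rise of 2, and none at 3. The Wilcoxon test, which has no covariate, starts at about 0.43 and loses about 17, 4 and 1 points.

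**Type I error.** With no effect, max(B, P) has the same distribution in both arms, so the test keeps its level.

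**The case against.** A reader might infer that the SAP departed from the protocol without listing the change in Section 11. The documents do not support that. A window starting from initial administration can be read either way for a wash taken just before dosing. SAP 10.1.1 openly states how the phrase is applied, with an example, and the AUC endpoints follow the same rule. The SAP says most efficacy endpoints, so the time endpoints may differ. A likely reason, though the SAP gives none, is that time to peak subtracts the first-dose time, so a pre-dose peak would give a negative time.

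A second tempting inference is that a 34–50% loss of effect means a similar loss of power. It does not: the floor also reduces the variance, and ANCOVA power falls by about 6 points in that case.

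The size may also lie at the mild end. Dosing starts about 12 hours after a positive wash, with testing twice daily from Day 2, so many pre-dose values should be early in viral growth. Participants dosed by default on Day 5 evening had no positive qicPCR, so their floor should usually be low.

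Finally, the bias is conservative, the endpoint is secondary in an early-phase study, and the primary AUC is untouched. All of this limits the weight of the point. What stands is the one-directional shrinkage of the estimate and the two meanings of peak within one section.

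**Conclusion.** The point holds as an avoidable dilution and an internal inconsistency. It is neither an undeclared protocol deviation nor a threat to the false-positive rate. By definition, the pre-dose sample in the window can only shrink a true reduction in peak load, and covariate adjustment does not restore it. How much depends on how far load still rises after the pre-dose sample, which the documents do not state: negligible if placebo rises about 3 log10, moderate at 2, and a third to a half of the effect at 1, given an SD of the rise of 1.2 log10 and true effects of 1 to 2 log10. The cost in ANCOVA power is small; under the Wilcoxon fallback it is noticeable when the rise is only 1 log10. A change is worth making because it is cheap and improves the estimate.

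**What to change.** Before unblinding:

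- In the two peak viral load paragraphs of SAP 10.7.2.3 (qRT-PCR and culture), define the peak as the highest value in samples collected after the first dose up to Day 12 am. Keep the pre-dose value only as the covariate.
- Record the exception to the 10.1.1 convention in Section 11, and report the current definition as a sensitivity analysis.
- Correct the time-from-peak derivations. The qRT-PCR text describes "The time from the peak qRT-PCR measurement after administration of IMP to the first confirmed negative qRT-PCR test" but computes "Date and time of first confirmed negative test – Date and time of first IMP administration", which does not start at the peak. The culture formula has the same fault. Both should subtract the time of the peak.
- Supply the derivation of time to peak viral culture. It is listed in SAP 7.2 and added by Section 11, but the last block of 10.7.2.3 repeats the qRT-PCR text.

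The cost is a few sentences and minor programming; no new data are needed. There is a small downside: the peak window no longer starts at the same sample as the AUC, and for a participant already declining at dosing the peak is simply the first post-dose value. The sensitivity analysis covers readers who prefer the current window.

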
 To evaluate the effect of RV299 compared to placebo in healthy adult participants inoculated with RSV in terms of antiviral effect assessed by: 
 Viral-load related endpoints. 	
Additional viral load endpoints relating to antiviral effect include, but are not limited to:
 
 Peak viral load of RSV as defined by the maximum viral load determined by qRT-PCR measurements in nasal samples starting from initial administration of IMP up to planned discharge from quarantine (Day 12, am). Time (days) to confirmed negative test by qRT-PCR measurements in nasal samples starting at initial administration of IMP to first confirmed undetectable assessment after peak measure. Time (days) to confirmed negative test by qRT-PCR measurements in nasal samples starting from peak qRT-PCR after initial administration of IMP to first confirmed undetectable assessment after peak measure. Time (days) to peak qRT-PCR in nasal samples, starting from initial administration of IMP. Area under the viral load-time curve (VL-AUC) of RSV challenge virus as determined by viral culture on nasal samples, starting at initial administration

Objectives	Endpoints
	
of IMP up to planned discharge from quarantine (Day 12, am).
 
 Peak viral load of RSV as defined by the maximum viral load determined by viral culture measurements in nasal samples starting from initial administration of IMP up to planned discharge from quarantine (Day 12, am). Time (days) to confirmed negative test by viral culture measurements in nasal samples starting at initial administration of IMP to first confirmed undetectable assessment after peak measure. Time (days) to confirmed negative test by viral culture measurements in nasal samples starting from peak viral culture after initial administration of IMP to first confirmed undetectable assessment after peak measure.

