11. CHANGES TO THE PROTOCOL SPECIFIED ANALYSIS DETAILED IN THE STATISTICAL ANALYSIS PLAN

1. Clarity has been added to the definitions for the ITT-A and ITT-B populations to ensure they are mutually exclusive and are accounting for subjects who have a positive detection either side of IMP administration.
2. The protocol incorrectly used median AUC as the main estimator of the primary endpoint. This has been corrected within the SAP to use the mean AUC.
3. Inferential analysis was not required for any time to event secondary endpoints within the protocol. However, this have been deemed as necessary to support the study outcome and log rank tests have been added to the appropriate endpoints.
4. The endpoint 'Time (days) to peak viral culture in nasal samples, starting from initial administration of IMP' had been missed in the list of endpoints within the protocol, though referred to in later sections. This endpoint has been added to the SAP.
5. Symptom resolution was included within the wording of the secondary clinical-symptom related endpoints and referred to as 'returning to baseline score'. This was deemed not to fit the requirements of the endpoint and has instead been amended to be 24-hours symptom free.
6. The endpoint 'Time to symptom resolution ... starting at initial administration of IMP to time of returning to baseline score' has been expanded to include the caveat that the symptom-free period must occur after the peak symptom score.

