Table 14.2.2.5.4	AUC of RSV Challenge Virus Viral Load by Viral Culture from Initial Administration of IMP to Quarantine Discharge (Untransformed Data) - ITT-I Population
Table 14.2.2.6	Peak Viral Load of RSV Challenge Virus by Viral Culture from Initial Administration of IMP to Quarantine Discharge - ITT-I Population

Where appropriate, these tables may be repeated on the ITT-A, ITT-B, ITT and PP Populations as .2, .3, .4 and .5 respectively.

Programming Note: It is possible that the parametric methods will fail to meet the required assumptions for the main or repeated tables. Therefore, we will provide a Wilcoxon test (see Section 10.1.4). The alternative presentation for this is shown below and will require the following footnote to be updated: [1] Comparison of RV299 and placebo using a Wilcoxon rank sum test.

Median difference in LS means [1] XX.XX
P-value [1] X.XXX

Table 14.2.2.2.1
Time to First Confirmed Undetectable Assessment of RSV Challenge Virus by qRT-PCR from Initial Administration of IMP
ITT-I Population

Time (days)	Treatment Group					
	RV299 (N=xx)			Placebo (N=xxx)		
	n	N#	Kaplan-Meier Estimate	n	N#	Kaplan-Meier Estimate
X	xx	xx	0.xxxx	xx	xx	0.xxxx
X	xx	xx	0.xxxx	xx	xx	0.xxxx
X	xx	xx	0.xxxx	xx	xx	0.xxxx
X	xx	xx	0.xxxx	xx	xx	0.xxxx
X	xx	xx	0.xxxx	xx	xx	0.xxxx
X	xx	xx	0.xxxx	xx	xx	0.xxxx
X	xx	xx	0.xxxx	xx	xx	0.xxxx
X	xx	xx	0.xxxx	xx	xx	0.xxxx
X	xx	xx	0.xxxx	xx	xx	0.xxxx
X	xx	xx	0.xxxx	xx	xx	0.xxxx
X	xx	xx	0.xxxx	xx	xx	0.xxxx
X	xx	xx	0.xxxx	xx	xx	0.xxxx
X	xx	xx	0.xxxx	xx	xx	0.xxxx
25 th percentile [1]		xx.x			xx.x	
50 th percentile [1]		xx.x			xx.x	
75 th percentile [1]		xx.x			xx.x	
p-value [2]		xxxxx				

n = number of participants with a confirmed undetectable assessment by the end of the period. N# = number of participants at risk.

[1] Percentiles are obtained from the Kaplan-Meier estimates.

[2] P-value obtained from a log-rank test compared RV299 and placebo.

Note: Time to First Confirmed Undetectable Assessment from Initial Administration of IMP = (Date of first confirmed negative test after peak qRT-PCR measurement - Date of first administration of IMP) + 1.

This table may be repeated on the ITT-A, ITT-B, ITT and PP Populations as .2, .3, .4 and .5 respectively.

This layout will be utilised for the following tables:

Table 14.2.2.3.1 Time to First Confirmed Undetectable Assessment of RSV Challenge Virus after Peak Measure by qRT-PCR from qRT-PCR following Initial Administration of IMP - ITT-I Population

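### The two time-from-peak-to-negative endpoints subtract the first-dose time instead of the peak time, and the related viral culture endpoints are inconsistently specified

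*SAP*

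**What the plan says.** Protocol Section 3 defines the qRT-PCR endpoint as running "starting from peak qRT-PCR after initial administration of IMP to first confirmed undetectable assessment after peak measure", and defines a parallel endpoint for viral culture. SAP Section 7.2 repeats both. In SAP Section 10.7.2.3 the headings and opening sentences also start the clock at the peak. The formulas beneath them do not:

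- qRT-PCR, from peak: "Date and time of first confirmed negative test – Date and time of first IMP administration".
- Viral culture, from peak: "Date of and time first confirmed negative test – Date and time of first IMP administration".

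The Kaplan-Meier plot described for each has an axis in days from first dose.

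Three related passages also conflict:

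- **Negative culture.** In the endpoint that starts at first dose, "A negative test is defined as a 'Not Detected' result in the viral culture test". In the endpoint that starts at the peak, "A negative test is defined as two consecutive 'Not Detected' results in the viral culture test".
- **Time to peak viral culture.** SAP Section 7.2 lists this endpoint. Section 11, item 4, says of it: "This endpoint has been added to the SAP". Section 13.2 gives it Table 14.2.2.9. In the place in Section 10.7.2.3 where its derivation belongs, the heading is "Time to Peak qRT-PCR in Nasal Samples Starting from Initial Administration of IMP", and the text repeats the qRT-PCR derivation.
- **Shell note.** The note to Table 14.2.2.2.1 in Section 14 computes the time as ("Date of first confirmed negative test after peak qRT-PCR measurement - Date of first administration of IMP) + 1", whereas the text takes a difference of dates and times and adds nothing.

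**The concern.** A from-peak endpoint exists to separate the speed of clearance from the time taken to reach the peak. If it is timed from first dose, that separation is lost. A treatment that only moved the peak could appear to change clearance, and a real change in clearance could be masked by an opposite shift in the peak.

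The SAP attaches a log-rank p-value to each of these endpoints. Section 11, item 3, adds those tests to support the study outcome. A p-value would therefore be reported under a label that does not match what was tested. The formula, the axis and the shell note are what a programmer works from, and all three point to first dose.

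**Working it through.** The documents give no planning figure for these endpoints, so there is nothing to reproduce. The check sets the definitions side by side, works an example and adds one illustrative simulation.

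**1. Origin of the clock.** Let D be first dose, P the post-dose peak and N the first confirmed negative after the peak.

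- From dose (SAP 10.7.2.3): N − D.
- From peak, as headed: N − P.
- From peak, as the formula stands: N − D.
- Error: (N − D) − (N − P) = P − D, which is the participant's time to peak.

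**2. Illustrative participant** (invented; mornings as whole days, evenings as half days): D = 2.5, P = 5.0, N = 9.0.

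- From dose: 9.0 − 2.5 = 6.5 days.
- From peak, as the formula stands: 9.0 − 2.5 = 6.5 days.
- From peak, as headed: 9.0 − 5.0 = 4.0 days.
- Excess: 6.5 − 4.0 = 2.5 days = 5.0 − 2.5.

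Both qRT-PCR endpoints use two consecutive 'Not Detected' results, so their event times coincide when the negative is taken after the peak, as the heading requires.

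**3. Error or choice?** The symptom-resolution endpoint from peak in SAP 10.7.2.4 does subtract the time of the peak score. Listings 16.2.6.1.2 and 16.2.6.2.2 have separate columns for time from dose and time from peak. Section 11 lists changes to the protocol analysis, and a change of origin is not among them. This points to a copying error.

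**4. Culture rule.** Suppose the first isolated negative after the peak comes 4.0 days after dose, is followed by positives, and the first of two consecutive negatives comes at 6.0 days. The one-result rule gives 4.0 days and the two-result rule 6.0 days, a difference of 2.0 days that comes from the definition alone.

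**5. Shell note.** For the participant in step 2, calendar days plus one give 9 − 2 + 1 = 8 days, against 6.5 from the text. The extra 1.5 days is the constant 1 plus 0.5 from dropping clock times. The same layout is assigned to the from-peak tables. Table 14.2.2.9 is not among the tables assigned to it and has no other shell.

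**6. Effect on the log-rank test, illustration only.** Assumptions not taken from the documents: 28 infected per arm (28/40 = 70%), time to peak mean 2.5 days (SD 1.0), post-peak clearance mean 4.0 days (SD 1.5), first dose spread evenly from Day 2 evening to Day 5 evening, 12-hourly sampling, censoring at Day 12 morning (simpler than the SAP rule of last detectable assessment), 2,000 runs, two-sided 5%.

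| Assumed treatment effect | Rejection, formula as written | Rejection, clock at peak |
|---|---|---|
| None | 5.8% | 5.8% |
| Peak 1 day earlier, clearance unchanged | 42% | 5% |
| Clearance 1 day faster, peak unchanged | 47% | 61% |
| Clearance 1 day faster, peak 1 day later | 6% | 49% |

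The percentages move with the assumptions. The pattern follows from step 1: the formula can create or hide a difference in post-peak clearance.

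**The case against.** The strongest defence is that the intent is plain. The protocol, the SAP headings and prose, the table titles and the listing columns all say from peak, so a careful programmer would notice. These are secondary endpoints in a Phase 1b study without multiplicity control. Protocol Table 9-2 plans no inferential test for the time-to-negative endpoints and does not list the qRT-PCR from-peak endpoint. All of this stands and bears on severity. It does not remove the contradiction, because no passage corrects the formulas or the axes.

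Some stronger readings are tempting but unsupported:

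- *The qRT-PCR from-peak analysis simply duplicates the from-dose one, p-value included.* That needs the words 'after peak' to be read into the from-peak formula, which omits them. Taken literally, a participant dosed on Day 5 evening without a positive qicPCR could have two 'Not Detected' results after dosing but before a later peak, and the two formulas would then differ.
- *The culture from-peak time can never be shorter than the from-dose time.* Censoring breaks this. Take first dose on Day 2 evening, virus last detected on Day 11 evening and 'Not Detected' on Day 12 morning. From dose this is an event at 12.0 − 2.5 = 9.5 days. From peak, with two negatives required, it is censored at 11.5 − 2.5 = 9.0 days.
- *The overstatement can be put at a given number of days or a percentage.* The documents give no viral kinetics, so only the algebraic statement is supported.
- *Culture clearance must require two negatives.* The visible protocol text says confirmed but gives no number.
- *Time to peak viral culture is undefined.* It is named, peak culture is defined, and a table and listing column exist. What is missing is the derivation and a table shell.

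**Conclusion.** The point holds as an internal contradiction that would produce wrong secondary results if programmed as written. For events after the peak, each from-peak value is too large by exactly that participant's dose-to-peak interval, and post-peak clearance is not estimated for either assay. The effect on the log-rank test can go in either direction, and its size rests on kinetics that would have to be assumed.

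The one-versus-two rule for culture and the missing culture derivation are confirmed. The shell note is minor: the constant day leaves the log-rank test unchanged and shifts percentiles equally in both arms, although dropping clock times adds rounding and ties.

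A reader might infer that the main efficacy conclusion is at risk. It is not, because the primary AUC uses none of these formulas. Severity: should fix.

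**What to change.** Before unblinding:

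1. In both from-peak sections, compute the date and time of the first confirmed negative after the peak minus the date and time of the post-dose peak. State 'after the peak' in the formula itself, and label the Kaplan-Meier axis as days from peak.
2. State one confirmed-negative rule for both culture endpoints. Two consecutive 'Not Detected' results would match the qRT-PCR endpoints, but the sponsor must choose.
3. Replace the repeated qRT-PCR time-to-peak text with the derivation for viral culture, and assign Table 14.2.2.9 a shell.
4. Align the note under Table 14.2.2.2.1 with the date-and-time formula in the text, and give the from-peak tables that share its layout a note with the peak as origin.

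The cost is SAP wording and shell edits, with no new data or assessments. The same correction made after unblinding could look data-driven.
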